16.0 REFERENCES

1.0 OBJECTIVES

1.1 Primary endpoint: Complete remission (CR) or complete remission with incomplete count recovery (CRi) rate at 24 months.

1.2 Secondary endpoints:

- 1. Progression-free survival (PFS) at 2 years.
- 2. Overall response rate (ORR) at 6, 12 and 24 months, CR/CRi rate at 6 and 12 months.
- 3. Time to best response.
- 4. Time to alternative treatment.
- 5. Overall survival at 5 years.

1.3 Exploratory endpoints:

- 1. Effect of ibrutinib treatment on immune function.
- 2. Effect of ibrutinib on frequency of subclonal driver mutations.
- 3. Incidence of emergence of subclonal resistance mutations (e.g. C481S mutation in *BTK* and mutations in *PLCG2*).

2.0 HYPOTHESES

- 1. We will see a high overall response rate, of approximately 90%, similar to that seen in first line treatment of CLL.
- 2. We anticipate seeing a higher rate of complete remission than in treatment of first-line CLL, given patients will have a lower disease burden. In the early report of a large, phase III study of ibrutinib in the first line setting, the CR/CRi rate was 4%, but this increased to approximately 16% after 2 years of follow-up (Pharmacyclics, internal data). We would expect the CR/CRi rate to potentially double when we treat patients early in their disease course; thus, we anticipate a complete remission rate at 2 years of approximately 30%.
- 3. We anticipate approximately 10-15% of patients will stop therapy due to toxicity. In the phase III study mentioned above, the treatment discontinuation rate was 9% at a median follow-up of 18 months. We expect that in an early treatment population, the rates of discontinuation may be somewhat higher, as there may be less willingness from patients and physicians to tolerate troublesome side effects.
- 4. We anticipate that ibrutinib will have beneficial effects on immune function, including improvement in immunoglobulin levers, including IgA(1) and T-cell function.
- 5. We anticipate a low rate of development of resistance mutations.

3.0 BACKGROUND AND RATIONALE

3.1 Clinical course of CLL.

CLL is the most common leukemia in the United States and Western hemisphere.(2) There is remarkable clinical diversity in patients with CLL. Following diagnosis, some patients have smoldering, asymptomatic disease that may not progress for many years, others are diagnosed with advanced stage and still others are diagnosed with early stage disease that rapidly progresses, causing symptoms and/or bone marrow failure and require treatment. Wierda et al. developed a nomogram designed to predict the time to first treatment for previously untreated CLL patients who did not have an indication for treatment at their initial assessment.(3) Patients with increased cervical lymph node size, unmutated *IGHV* gene, elevated LDH, ≥3 involved lymph node sites, del(11q) or del(17p) demonstrated more rapid disease progression, with shorter time-to-first-treatment.(3)

3.2 Studies of early versus deferred treatment in CLL.

No study has demonstrated a survival benefit for early versus deferred treatment in CLL, although the initial studies were done with alkylating agent-based treatment, which would be considered ineffective given current standards of care. Also, historic trials included all patients and did not have reliable tools to screen out low-risk patients who may never need treatment. Two large French studies definitively demonstrated a lack of survival benefit for early versus deferred treatment with chlorambucil monotherapy,(4) while a large meta-analysis also showed no survival benefit for early treatment with either chlorambucil or anthracycline-based chemotherapy.(5) More recently, a German-French co-operative study showed event-free survival, but not overall survival benefit for early treatment with FCR, although follow-up was short.(6) Given the lack of demonstrable survival benefit with early therapy, early-stage CLL is managed with "watchful waiting". Patients are considered for treatment only if significant disease-related symptoms or marrow failure develop.(7) The lack of survival benefit seen in early therapy studies, despite prolonged PFS, also relates to a combination of toxicity from chemotherapy, as well as inability to eradicate the CLL clone with the result that the disease is less treatment-sensitive at relapse. Therefore, these older trials lacked our current understanding of high-risk features, including low-risk patients, and utilized ineffective therapies, which probably contributed to the negative findings.

3.3 Early-stage CLL is associated with increased infection risk and a higher incidence of other cancers.

Even untreated, early stage CLL or its precursor condition, monoclonal B-cell lymphocytosis (MBL), are associated with significant infection risk(8, 9) and infection remains a leading cause of morbidity and mortality in CLL. In addition, there is an increased incidence of other hematologic(10, 11) and non-hematologic cancers(12, 13) in patients with even early-stage CLL or high-count MBL. Treatment with a non-immunosuppressive, non-genotoxic agent, may potentially reduce these risks.

3.4 Adverse effects of chemotherapy-based treatment in CLL.

Patients with CLL have a higher risk of second cancers, particularly skin, AML/MDS and Richter transformation.(14) While the impact of specific therapy is controversial, it was suggested that fludarabine-based treatment may increase the risk of Richter transformation(15) (and [name], unpublished data). Fludarabine-based chemotherapy is also associated with myelosuppression, lymphocyte depletion, and infection risk.(16) Therefore, delay of initiation of chemoimmunotherapy is a desirable goal. Early studies were conducted prior to the availability of highly-effective, non-myelosuppressive and non-mutagenic agents, such as ibrutinib. Although data is currently lacking, early treatment with ibrutinib could reasonably be expected to result in a lower incidence of both treatment-related infectious complications and second cancers relative to chemoimmunotherapy.

3.5 Ibrutinib as first-line therapy in CLL.

lbrutinib demonstrated remarkable efficacy in first-line treatment of CLL in elderly patients.(17) Treatment was well tolerated, with few serious adverse events. Mild diarrhea was the most common adverse event,(17) but generally self-limited. Grade 3 toxicity requiring temporary treatment interruption was seen in 29% of patients, but no patient permanently ceased treatment due to toxicity. Of 31 patients, with a median follow-up of 22 months, only 1 patient progressed; this patient, who had del(17p), developed Richter transformation after approximately 6 months on treatment. In this study 96% remained progression-free at 24 months. More recently, the RESONATE-2 study demonstrated a survival benefit relative to chlorambucil and an impressive 90% PFS at 18 months, leading to first line approval of ibrutinib by the U.S. Food and Drug Administration. Rare, but serious adverse events include atrial fibrillation, which occurred in approximately 6% of patients in the ibrutinib arm; minor bleeding is more common in ibrutinib-treated patients, but major bleeding is rare.(18) An update of this study at ASH 2016 demonstrated increasing rate of CR/CRi over time and 89%

PFS at 24 months, with 79% of patients remaining on therapy at a median follow-up of 28.5 months.(19)

3.6 Resistance to ibrutinib therapy.

Resistance mutations developed during ibrutinib therapy in relapsed/refractory patients, particularly those with del(17p) and complex karyotype. It could be postulated that early treatment, when patients have a lower total disease burden, may result in lower incidence of resistance mutations and superior responses.

3.7. Potential advantages of early therapy with ibrutinib.

Ibrutinib therapy may have beneficial effects on immune function, by inhibiting ITK and skewing T cell responses to T_H1-type;(20) Ibrutinib also reduces PD1/PDL1 expression on CLL cells and PD1 expression on T cells(21) and enhances *in vitro* response to viral peptides ([name], [name] and [name], manuscript submitted). Notably, during continued long-term therapy, infections are noted more frequently within the first year of treatment than subsequently.(22) Improvement in IgA levels(1) has also been seen in patients treated with ibrutinib.

At the time of treatment patients with CLL have significant intra-tumor clonal heterogeneity, with multiple sub-clones, notable for different driver mutations. Treatment with cytoreductive therapy, particularly cytotoxic chemotherapy, results in selection of aggressive subclones, such as those with *TP53* mutation;(23) clones containing *TP53* mutation invariably predominate at relapse, even if their initial frequency is low.(24) CLL cells containing chromosomal abnormalities or mutations which confer resistance to conventional cytotoxic chemotherapy (e.g. del(17p)) show similar sensitivity to novel therapies such as ibrutinib, compared to CLL cells lacking these deleterious mutations.(25, 26) However, during long-term therapy, such patients are more likely to develop novel mutations such as the C481S mutation in *BTK* and activating mutations in *PLCG2*, conferring ibrutinib resistance.(26) To the limits of sensitivity of available testing, these mutations do not pre-date ibrutinib therapy and are thus thought to develop during therapy.(25) Early treatment, at a time when the total burden of CLL cells containing deleterious mutations is likely low, presumably will reduce the mathematical likelihood that a subclone containing an ibrutinib resistance mutation will develop.

3.8 Toxicity of the proposed regimen.

Toxicities associated with ibrutinib are discussed in detail in section 6.4.5. Ibrutinib is generally well-tolerated and over 90% of patients remained on therapy at 18 months of follow-up. The most commonly reported AEs are diarrhea, fatigue, cough and nausea, which are generally mild and not treatment-limiting. In the first line setting, 2.5% of patients had grade 3-4 hemorrhage and 6% developed atrial fibrillation.(18)

4.0 STUDY POPULATION

4.1 Inclusion criteria.

- 1. Diagnosis of CLL/SLL that meets IWCLL diagnostic criteria.(7)
- Patients must be aged over 18 years at the time of informed consent, understand and voluntarily sign an informed consent, and be able to comply with study procedures and follow-up examinations.
- 3. No treatment indication according to IWCLL criteria.(7)
- 4. Estimated time to first treatment of 3 years or less according to MDACC nomogram.(3)
- 5. ECOG performance status of 0-2.(27)
- 6. Male and female subjects who agree to use both a highly effective method of birth control (e.g., implants, injectables, combined oral contraceptives, some intrauterine devices [IUDs], complete abstinence¹, or sterilized partner) and a barrier method (e.g., condoms, vaginal ring, sponge, etc.) during the period of therapy and for 30 days after the last dose of study drug for females and 90 days for males. OR Female subjects who are of non-reproductive potential (i.e., postmenopausal by history no menses for ≥1 year; OR history of hysterectomy; OR history of bilateral tubal ligation; OR history of bilateral oophorectomy).
- 7. Adequate hepatic and renal function as indicated by all of the following: Total bilirubin </=1.5 x institutional Upper Limit of Normal (ULN) except for patients with bilirubin elevation due to Gilbert's disease or of non-hepatic origin who will be allowed to participate; an ALT </=2.5 x ULN; and estimated creatinine clearance

About HMA/Working Groups/CTFG/2014 09 HMA CTFG Contraception.pdf

Protocol 2017-0039. Ibrutinib early treatment for high-risk CLL. Version 11, 19Dec2022

Page 8 of 43

¹ Complete abstinence is a highly effective method only if defined as refraining from heterosexual intercourse during the entire period of risk associated with the study treatments. The reliability of sexual abstinence needs to be evaluated in relation to the duration of the clinical trial and the preferred and usual lifestyle of the subject. http://www.hma.eu/fileadmin/dateien/Human_Medicines/01

- (CrCl) of > 30 mL/min, as calculated by the Cockroft- Gault equation unless disease related.
- 8. PT/INR <1.5 x ULN and PTT (aPTT) <1.5 x ULN (unless abnormalities are unrelated to coagulopathy or bleeding disorder).
- 9. Free of prior malignancies for 3 years with exception of patients diagnosed with basal cell or non-metastatic squamous cell carcinoma of the skin, or carcinoma "in situ" of the cervix or breast, who are eligible even if they are currently treated or were treated and/or diagnosed in the past 3 years prior to study enrolment.
- 10. A negative urine pregnancy test (within 7 days of enrollment date) is required for women with childbearing potential. Women of childbearing potential include any female who has experienced menarche and who has not undergone successful surgical sterilization (hysterectomy, bilateral tubal ligation, or bilateral oophorectomy) or is not postmenopausal (≥1 year of no menses, by history).

4.2 Exclusion criteria.

- Receipt of any prior therapy for CLL. Patients who have received "early intervention" with INVAC-1 vaccine against hTERT will be eligible provided all the following exist:
 - i) They had no response to the vaccine treatment (persistent CLL >1% in bone marrow).
 - ii) ≥3 months have elapsed since the last dose of vaccine.
 - iii) No residual toxicities attributable to the vaccine exist at the time of study enrollment.
 - iv) The patient does not meet IWCLL criteria for requiring treatment.
- 2. Richter transformation.
- 3. Active malignancy requiring systemic therapy, other than CLL, with the exception of: adequately treated in situ carcinoma of the cervix uteri; adequately treated basal cell carcinoma or localized squamous cell carcinoma of the skin; previous malignancy confined and surgically resected (or treated with other modalities) with curative intent.
- 4. Systemic anticoagulation with warfarin or other Vitamin K antagonists.
- 5. Active and uncontrolled autoimmune hemolytic anemia (AIHA) or autoimmune thrombocytopenia (ITP) requiring daily prednisone dose of >20 mg.
- 6. Current and concurrent use of strong CYP3A4 inhibitors or activators.
- 7. Pregnant or breast-feeding females.

- 8. Uncontrolled and active systemic fungal, bacterial, viral, or other infection (defined as exhibiting ongoing signs/symptoms related to the infection and without improvement, despite appropriate antibiotics or other treatment).
- Any other severe concurrent disease, or history of serious organ dysfunction or disease involving the heart, kidney, liver or other organ system that, in the investigator's opinion, may place the patient at undue risk to undergo therapy with ibrutinib.
- 10. Currently active, clinically significant cardiovascular disease, such as uncontrolled arrhythmia or Class 3 or 4 congestive heart failure as defined by the New York Heart Association Functional Classification; or a history of myocardial infarction, unstable angina, or acute coronary syndrome within 6 months prior to randomization.
- 11. History of ischemic stroke within 6 months prior to enrollment.
- 12. Evidence of bleeding diathesis or coagulopathy within 3 months (e.g., von Willebrand's disease or hemophilia).
- 13. Any history of symptomatic intracranial hemorrhage.
- 14. Major surgical procedure with 4 weeks of first dose of study drug; open biopsy, or significant traumatic injury within 7 days prior to enrollment date; anticipation of need for major surgical procedure during the course of the study.
- 15. Minor surgical procedures, fine needle aspirations or core biopsies within 3 days prior to enrollment date. Bone marrow aspiration and/or biopsy are allowed.
- 16. Serious, non-healing wound, ulcer, or bone fracture.
- 17. Vaccinated with live, attenuated vaccines within 4 weeks of first dose of study drug.
- 18. Active, uncontrolled infection.
- 19. Known history of human immunodeficiency virus (HIV) or active with hepatitis C virus (HCV) or hepatitis B virus (HBV). Subjects who are positive for hepatitis B core antibody, hepatitis B surface antigen, or hepatitis C antibody must have a negative polymerase chain reaction (PCR) result before enrollment. Those who are PCR positive will be excluded.
- 20. Currently active, clinically significant hepatic impairment Child-Pugh class B or C according to the Child Pugh classification (see Appendix L)

5.0 TREATMENT PLAN

5.1 Recommended prophylactic medications:

The following are recommended prophylactic medications. For individuals who are allergic, an equivalent replacement may be identified:

- Allopurinol 300 mg PO daily for the first 7 days of course 1 is recommended for tumor lysis prophylaxis.
- Valacyclovir 500 mg PO daily for all treatment courses and for at least 3 months after completion of treatment is recommended, for herpes virus prophylaxis.

5.2 Treatment regimen.

Ibrutinib monotherapy will be administered at 420mg once daily until either:

- 1. Disease progression or
- 2. Achievement of complete remission with negative MRD, on two separate assessments, at least 6 months apart. For the purposes of determining treatment cessation, MRD analysis must be performed on bone marrow, using standardized 4-color flow cytometry and demonstrate sensitivity of at least 0.01%.(28) We anticipate a low rate of MRD-negative CR/CRi, which may require prolonged treatment to achieve. Patients who discontinue ibrutinib due to achievement of MRD-negative CR/CRi, will continue to have routine clinical follow-up every 3 months, which will include MRD analysis in peripheral blood, performed at least once per year.
- 3. Completion of 2 years of therapy.

5.3 Long term follow-up.

Patients who remain on therapy at 2 years (the timing of the primary endpoint) may continue ibrutinib, at the discretion of their physician. This would, however, require transition to commercial supply of ibrutinib and should be discussed with the PI. If patients choose to have follow-up at M.D. Anderson, they will be seen every 3-6 months, at the discretion of their physician. If they are receiving follow-up at an outside center, they will be telephoned by study staff every 6 months (until disease progression, death or receipt of a new therapy) to determine:

- Whether they are still receiving study drug.
- Whether any significant toxicity has occurred.
- Whether their disease remains in remission.
- Whether they have had any other cancer therapy.

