- (8) Biochemistry. Serum chemistry consists of a peripheral blood draw with the following assessments: include serum sodium, potassium, calcium, BUN, creatinine, glucose,

phosphorous, magnesium, albumin, total protein, alkaline phosphatase, total bilirubin, ALT, uric acid, LDH, β-2 microglobulin, immunoglobulins.

- (9) CT of the neck, chest, abdomen and pelvis will be performed for response evaluation. If PET/CT or MRI was performed pre-treatment, this should be performed instead of CT scan, if available. If patients achieve complete remission by CT criteria (see section 11.0), subsequent CT scans can be omitted, per investigator discretion.
- (10) Bone marrow examination with CLL FISH panel and flow cytometry will be performed pre-treatment and at 6, 12, and 24 months. Conventional stimulated metaphase karyotyping will be performed at baseline and at disease progression, using local protocols. Pre-treatment, CLL FISH panel need not be repeated if performed at MDACC within the past year.
- (11) ECG. ECG will be done prior to treatment, in the routine diagnostic lab and then as clinically indicated.
- (12) Echocardiogram. ECHO or MUGA will be performed at screening (within 2 weeks of starting treatment) and at end of treatment or at 2 years, whichever is soonest. If a patient has undergone ECHO or MUGA as standard of care prior to entering the study, the procedures will not have to be repeated if results are available and the procedures were performed within 28 days of study entry.
- (13) Pregnancy test. The pregnancy test must be a beta-human chorionic gonadotropin (β-HCG) test, using either urine or serum. Women who are not of childbearing potential (status post-hysterectomy, status post-bilateral oophorectomy, or postmenopausal [defined as amenorrhea for at least 12 months]) do not need to have the test performed. If the test is deemed necessary, it must be performed within 7 days preceding the commencement of study therapy and known to be negative. Women of childbearing potential at study commencement must also complete the pregnancy test at the End-of-Treatment Visit.
- (14) QOL evaluation. Quality of life will be evaluated using the FACIT-Fatigue and EQ-5D-5L questionnaires pre-treatment, at 12 months, 24 months and at disease progression.

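### Section 5.3 ends the calls to outside-center patients at progression or new therapy, and no section schedules the later follow-up that 5-year OS and time to alternative treatment need

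*Combined protocol and SAP*

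**What the plan says.** Section 1.2 lists "Overall survival at 5 years" and "Time to alternative treatment" among the secondary endpoints.

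Section 5.3 is the only text on contact after year 2 for patients still on treatment. It opens with a restricted group: "Patients who remain on therapy at 2 years (the timing of the primary endpoint) may continue ibrutinib". Those who choose the study center are seen every 3-6 months, with no stopping event given. Those followed elsewhere are called "at an outside center, they will be telephoned by study staff every 6 months (until disease progression, death or receipt of a new therapy". One item on each call is "Whether they have had any other cancer therapy".

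Four other places bear on the point:
- Section 5.2 gives patients who stop for MRD-negative remission 3-monthly clinical follow-up.
- Section 10.0 has a visit calendar that ends at cycle 24 and a progression visit.
- Section 12.1.8, on new malignancies, counts survival follow-up after progression among the protocol's follow-up periods, with no interval, method or duration.
- Section 13.0 makes clinically significant progression a reason for removal from study and is silent on survival contact afterwards.

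Section 15.4 plans Kaplan-Meier curves and 2- and 5-year rates with 95% confidence intervals. It gives no censoring rule and does not name OS among the curves.

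**The concern.** Progression is the point at which one would expect the risks of next therapy and of death to rise. If scheduled contact ends there, the patients most likely to have either event leave observation just before it, which is informative censoring.

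The two stopping events act differently. Stopping at progression can affect both endpoints. Stopping at new therapy can affect OS only, because new therapy is itself the event for the other endpoint.

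The gap is wider than the call rule. Section 2.0 states "We anticipate approximately 10-15% of patients will stop therapy due to toxicity", and some patients will progress before month 24. Section 5.3 does not cover either group, so neither has a stated long-term follow-up.

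At stake are two descriptive secondary estimates. A larger sample would not remove the bias, and dates not collected at the time may be hard to recover.

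**Working it through.** **1. The plan's own figure.** The only design figure is 78% power (Section 15.2: n=50, 16% versus 30%, one-sided 0.05). Rejecting at 13 or more CR/CRi of 50 gives exact alpha 0.0475 and power 77.7%, so it reproduces. CR/CRi is read at 24 months, before Section 5.3 applies, so this point does not touch it.

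**2. Inputs for an illustration.**
- From Section 3.5: 24-month PFS of 89% (updated phase III first-line study) and, for the earlier study, "In this study 96% remained progression-free at 24 months".
- From Section 5.3: calls every 6 months; only progression at or after year 2 is affected.
- Assumed, because the documents give no figures: off-site share 25%, 50% or 100%; death hazard 0.01/yr before progression and 0.05, 0.10 or 0.20/yr after; mean lag from progression to next therapy 3, 6 or 12 months; on-treatment PFS continued at a constant rate to year 5; no alternative treatment without progression; censoring at last contact; no other source of events.

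**3. How many progress.** Total hazard a = -ln(PFS)/2; progression hazard p = a - 0.01; cumulative progression = (p/a)(1 - exp(-a·t)).
- 89%: a = 0.0583, p = 0.0483. Progression is 0.091 by year 2 and 0.209 by year 5, so 0.118 in years 2-5, about 6 of 50.
- 96%: a = 0.0204, p = 0.0104. Progression is 0.021 by year 2 and 0.050 by year 5, so 0.029 in years 2-5, about 1-2 of 50.

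**4. True 5-year OS at 89% PFS.** With post-progression death hazard d, S(5) = exp(-5a) + [p/(a - d)]·[exp(-5d) - exp(-5a)]. For d = 0.10: 0.747 + [0.0483/(-0.0417)]·(0.607 - 0.747), about 0.91. For d = 0.05, 0.10 and 0.20 the values are 93.1%, 91.0% and 87.6%.

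**5. Effect of the call rule.** I simulated 2,000,000 patients. Off-site patients progressing at or after year 2 are censored at the first call after progression; deaths and therapy starts before that call count. Alternative treatment is 1 minus Kaplan-Meier with deaths censored, at d = 0.10. Shifts are in percentage points; the OS range runs over d and the alternative-treatment range over the lag.

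| 24-month PFS | Off-site share | 5-year OS overstated | Alternative treatment understated |
|---|---|---|---|
| 89% | 25% | 0.1-0.5 | 1.0-1.3 |
| 89% | 50% | 0.2-1.0 | 2.0-2.6 |
| 89% | 100% | 0.5-2.1 | 4.0-5.3 |
| 96% | 25% | 0.03-0.14 | 0.3 |
| 96% | 50% | 0.07-0.27 | 0.5-0.7 |
| 96% | 100% | 0.13-0.55 | 1.0-1.3 |

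The true 5-year incidence of alternative treatment is 16.5-20.1% at 89% PFS and 3.8-4.7% at 96%. With d varied over 0.05-0.20, the 89%, 100% off-site range is 3.9-5.5.

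**6. Against sampling error.** Half-width = 1.96·sqrt(q(1-q)/50). At 89% PFS this is 7.0-9.1 points for OS of 93.1-87.6%, and about 10-11 points for an incidence of 16-20%.

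**7. Cross-check.** A separate three-state model with constant hazards took 20% of PFS events as deaths and ended contact at progression itself. At 89% PFS, half off-site and loss only after month 24, OS shifts by 0.2-1.9 points (annual death risk after progression 5-30%). Freedom from alternative treatment shifts by 2.4-6.0 points (median lag 24 to 3 months). The latter are upper values, because this model gives no credit for therapy found on the call that reveals progression. With no change in death hazard at progression, the OS bias is zero (94.3% either way).

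**The case against.** The strongest reply is that Section 12.1.8 shows survival follow-up after progression was intended, so this is an unscheduled intention and not a decision to stop. That stands as a description. A reader might infer that the plan deliberately abandons OS, that Section 13 ends survival contact, or that Section 15.4 censors at progression; no text says any of these. But intent without a schedule does not override the explicit stop in Section 5.3, and staff following that section would end the calls.

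A reader might also infer that the upward bias follows from the text alone. It does not. The text supplies only the stopping rule. The direction also needs a higher event risk after progression, no other route by which events become known, and censoring at last contact. The documents state none of these. If deaths reached the team passively while living patients were censored at their last call, the OS bias could weaken or reverse; no such route is described.

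It is tempting to express the alternative-treatment shift relative to its true incidence. That holds only if nobody switches without progressing. Section 5.3 names new therapy as a separate stop, and Section 3.5 reports 89% PFS at 24 months but 79% still on therapy at a median of 28.5 months. If 10-15% of patients also switched without progressing and were captured, the true incidence at 89% PFS would rise from 16-20% to about 25-32%. The absolute shifts would shrink by only about 10-15% of their size, but the relative figures would fall sharply. They should not be quoted.

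The PFS extrapolation is fragile too. Protocol treatment ends at 2 years, continuing needs commercial supply, and both source cohorts were first-line patients, not patients without a treatment indication. The error could go either way. The 100% off-site row is an extreme, since study-center visits have no stated stop.

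**Conclusion.** The textual gap is clear, and confidence in it is high: two declared secondary endpoints need data after progression, Section 5.3 ends off-site contact at progression, and nothing else schedules that contact. Both estimates are likely to be too favourable under the three conditions above.

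Confidence does not extend to the size. The table is an illustration, and every shift in it is smaller than the corresponding sampling error at n=50; the effect on OS is small. Losing patients who progress before year 2 as well would enlarge the bias. That would come from the absence of any stated follow-up for them, not from the call rule, and the table leaves it out.

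Nothing supports reading this as a threat to the primary endpoint, its test or its power. It should be fixed, but at the lower end of that category.

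**What to change.** Reconcile Sections 5.3, 12.1.8 and 13, and complete 15.4:
- **5.3:** collect vital status and the start date of the first next CLL therapy every 6 months for every enrolled patient, regardless of progression, new therapy, treatment status or place of follow-up. Continue until death, withdrawal of consent or at least 5 years from first dose, without shortening any existing follow-up.
- **12.1.8:** refer to that schedule.
- **13:** state that removal from study does not end this contact unless consent is withdrawn.
- **15.4:** name OS among the Kaplan-Meier endpoints, and censor OS and time to alternative treatment at last contact.

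The cost is wording plus short calls by the same staff. At 89% PFS, 0.209 × 50 gives 10-11 patients progressing by year 5, plus 5-8 stopping for toxicity (10-15% of 50), so roughly 15-19. At 96% PFS it is 2-3 plus 5-8, so roughly 7-11. Fewer extra calls are needed if many patients are seen at the study center. The change affects data collection only, not treatment.
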